4.1.2.2 Key secondary endpoints (alpha controlled)

The following key secondary endpoints, which will be tested in hierarchical order (see section 4.1.3.1), are defined:

 Extent of disease control defined as the number of cumulative weeks over the planned 24-week treatment period with platelet counts of ≥50×109/L in the chronic ITP population.

Derivation: total number of analysis visits during the treatment phase with platelet counts of $\geq 50 \times 10^9$ /L.

Handling of intercurrent events will be as follows:

- early discontinuation of treatment (prior to week 24) due to lack of efficacy or due to an AE: platelet count measured strictly after this intercurrent event will be handled as <50×10⁹/L.
- increase of dose and/or frequency of concurrent ITP therapies or start of a new concurrent ITP therapy: platelet count measured strictly after this intercurrent event will be handled as <50×10⁹/L.

SGS	Statistical Analysis Plan	
ARGX-113-1801	Final analysis	Final 1.0 of 28MAR2022

• initiation of rescue therapy: platelet count measured in the 4 weeks strictly following this intercurrent event (start of the administration of the first rescue treatment of every different occurrence initiation) will be handled as $<50 \times 10^9$ /L.

Note: the platelet count on the start date of the different intercurrent events will be used as is, imputation will only start on the next day

Missing values for reasons other than the main intercurrent events, will be imputed as described in section 4.1.2.5 (approach 1). The main analysis (alpha-controlled) on the first key secondary endpoint extent of disease control will use the composite variable strategy as described above in case of main intercurrent events using the stratified Mann-Whitney test (see also section 4.1.3.4).

A first complementary analysis will be conducted using the stratified Mann-Whitney test where the main intercurrent events are handled differently, i.e. using the treatment policy strategy, where platelet counts are used to derive the endpoint regardless of whether or not the intercurrent event occurs.

A second complementary analysis will be conducted where extent of disease control is handled as a time-to-event endpoint (with "loss of disease control" being the event).

Loss of disease control is derived as defined in Table 4.

Situation	Time to Loss of Disease Control or Censoring	Outcome
No occurrence of platelet count of $\geq 50 \times 10^{9}/L$	0	Event
Early discontinuation of treatment (prior to W24)	Total number of analysis visits during the treatment phase with platelet counts of $\geq 50 \times 10^9/L$ up to date of treatment discontinuation	Event
Rescue therapy	Total number of analysis visits during the treatment phase with platelet counts of $\geq 50 \times 10^9$ /L up to date of initiation of rescue therapy (start of the administration of the first rescue treatment)	Event
Dose and/or frequency of concurrent ITP therapy increased	Total number of analysis visits during the treatment phase with platelet counts of $\geq 50 \times 10^9$ /L up to start date of increase	Event
Disease control at end of 24-week treatment period	Total number of analysis visits during the treatment phase with platelet counts of $\geq 50 \times 10^9$ /L up to date of last assessment (analysis visit)	Censored

 Table 4: Definition for Loss of Disease control

Missing values not due to one of the main intercurrent events will be handled as described in section 4.1.2.5 (approach 1).

SGS	Statistical Analysis Plan	
ARGX-113-1801	Final analysis	Final 1.0 of 28MAR2022

2) Proportion of patients with a sustained platelet count response (week 19 - 24) in the overall population (chronic and persistent ITP).

Derivation: A patient is considered a responder, i.e. has a sustained platelet count response, if he/she shows platelet counts of at least 50×10^9 /L for at least 4 of the 6 analysis visits between weeks 19 and 24 of the study. Intercurrent events will be handled with the same composite variable strategy as for the primary endpoint described in section 4.1.2.1. Missing values for reasons other than the main intercurrent events, will be imputed as described in section 4.1.2.5 (approach 1).

3) Incidence and severity of the WHO-classified bleeding events (overall population).

Derivation: total number of analysis visits for which WHO bleeding scale ≥ 1 . The overall score of the bleeding events per analysis visit will be used, calculated as the maximum bleeding scale over the different body systems available per analysis visit. The data will be used as is, without taking into account intercurrent events (treatment policy strategy). Missing bleeding assessments after one of the main intercurrent events will not be imputed. For 'increase of dose and/or frequency of concurrent ITP therapies or start of a new concurrent ITP therapy' and 'initiation of rescue therapy' the whole treatment period should be taken into account. In case of rescue therapy, the bleeding events will not be imputed for 4 weeks strictly after the initiation of the therapy (the initiation of the therapy is the start date/time of the administration of the first rescue treatment for that occurrence). Missing values for reasons other than the main intercurrent events, will be imputed as described in section 4.1.2.5 (approach 3).

4) Proportion of patients achieving platelet counts of at least 50×109/L for at least 6 of the 8 visits between weeks 17 and 24 of the study in the overall population.

Derivation: A patient is considered a responder if he/she shows platelet counts of at least 50×10^9 /L for at least 6 of the 8 analysis visits between weeks 17 and 24 of the study. Intercurrent events will be handled with the same composite variable strategy as described in section 4.1.2.1. Missing values not due to intercurrent events will be handled as described in section 4.1.2.5 (approach 1).

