4.1.3.7 Cox Proportional Hazards Regression

The Cox proportional hazard model will be used to calculate the estimate of the hazard ratio (HR) and 95% confidence interval for the treatment effect of the extent of disease control as complementary analysis for the first key secondary endpoint (see section 4.1.2.2), and the time to platelet count response (see section 4.1.2.3).

The model will include treatment as fixed effects, with baseline platelet level and stratification factors as covariates. The HR for efgartigimod vs. placebo will be provided, along with the associated 95% 2-sided Wald-type CI and 2-sided p-value.

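### SAP Table 4 censors a fully known count of controlled weeks by week-24 status and leaves some completers without a row (complementary analysis, outside alpha control)

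*SAP*

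**What the plan says.** The first key secondary endpoint is a count over 24 weeks. SAP 4.1.2.2 gives it as "Derivation: total number of analysis visits during the treatment phase with platelet counts of" at least 50×10⁹/L. The main, alpha-controlled test is the stratified Mann-Whitney test on that count (SAP 4.1.3.4).

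Protocol 8.4.2 also plans a time-to-event version and leaves its event and censoring scheme to the SAP. SAP 4.1.2.2 supplies it: "A second complementary analysis will be conducted where extent of disease control is handled as a time-to-event endpoint", with loss of disease control as the event. SAP 4.1.3.7 fits a Cox model to it as "complementary analysis for the first key secondary endpoint", and SAP 4.1.3 adds Kaplan-Meier estimates by arm. The rows of Table 4 are:

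| Situation | Time | Outcome |
|---|---|---|
| "No occurrence of platelet count of" at least 50×10⁹/L | 0 | Event |
| Treatment stopped before week 24 | Controlled visits up to the stop | Event |
| Rescue therapy | Controlled visits up to first rescue | Event |
| Concurrent ITP therapy increased | Controlled visits up to the increase | Event |
| "Disease control at end of 24-week treatment period" | Controlled visits up to last assessment | Censored |

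**The concern.** In every row the time is a tally of controlled visits, not elapsed time. For a patient who completes 24 weeks, nothing about that tally remains to be observed. Censoring tells the Kaplan-Meier and Cox methods that the true value is this number or more. Here the value is exactly this number, and what triggers the censoring (platelet status at week 24) is itself one of the visits being counted.

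Table 4 is also incomplete:

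- No row covers a completer with some counts of at least 50, no intercurrent event, and a count below 50 at week 24.
- Control at the end of treatment is not defined.
- No precedence is stated when two rows apply, for example rescue early on and control at week 24.
- The therapy-increase row does not name the start of a new concurrent ITP therapy, which the main analysis in the same section treats as an intercurrent event.

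At stake is a hazard ratio and a Kaplan-Meier table that would be read as support for the first key secondary endpoint without estimating cumulative weeks of control.

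**Working it through.** **The plan's own figure.** SAP 1.4 states more than 99% power at N = 117, and N = 54 for 90% power, for the Mann-Whitney test with medians 10 v 3 and 2:1 allocation. The spread is not given. If counts are assumed exponential, P(efgartigimod > placebo) = 10/13 = 0.769. Noether's formula then gives N = (1.960 + 1.282)² / (12 × 2/9 × 0.269²) = 54.4, and 99.7% power at 117. With the O'Brien-Castelloe approach, which the SAP cites, an assumed normal spread with SD 7 gives N = 52.0 (54 when rounded up for 2:1) and exponential counts give 46. The figure is thus reproducible under plausible spreads. No figure is stated for the time-to-event version.

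**Same count, different outcome.** Patient A is controlled at weeks 20 to 24 only, so Table 4 censors A at 5. Patient B has 5 controlled weeks early and is rescued at week 21, so B is an event at 5. The main analysis gives both a count of 5.

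**Direction for Kaplan-Meier.** S(t) = ∏(1 − dᵢ/nᵢ). Relabelling an event as censored at the same count leaves every nᵢ unchanged and can only lower dᵢ. The curve therefore rises or stays where it is. Example with ten counts (c = censored): 0, 2, 5c, 8c, 8, 10, 12c, 18c, 20c, 22c.

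- Observed median: (8 + 10)/2 = 9.
- Kaplan-Meier: 9/10 = 0.900; × 8/9 = 0.800; × 6/7 = 0.686; × 4/5 = 0.549. All later values are censored, so the median is not reached.

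**Size.** The documents give no distribution, so everything below is assumption. Weekly states were simulated with patient-level propensity, varying persistence, spread and intercurrent-event frequency, and calibrated to medians of about 10 v 3 (90,000 patients per scenario). E = efgartigimod, P = placebo.

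| Intercurrent event, E/P | Observed median, E/P | KM median under Table 4, E/P | No row, E/P | HR, all counts observed | HR, Table 4, no-row = event | HR, Table 4, no-row = censored |
|---|---|---|---|---|---|---|
| 13/17% | 10/3 | 13/3 | 31/34% | 0.561 | 0.510 (−9.1%) | 0.511 |
| 32/40% | 10/3 | 12/3 | 21/24% | 0.586 | 0.549 (−6.3%) | 0.571 |
| 48/60% | 10/2 | 11/2 | 12/14% | 0.618 | 0.589 (−4.7%) | 0.611 |
| 31/36% | 9/3 | 12/3 | 13/14% | 0.801 | 0.734 (−8.4%) | 0.730 |
| 32/40% | 10/3 | 12/3 | 17/20% | 0.641 | 0.608 (−5.1%) | 0.653 |
| 13/14% | 10/3 | 14/3 | 13/13% | 0.848 | 0.793 (−6.5%) | 0.779 |

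The KM medians count patients without a row as events; percentages in brackets are the change from the all-observed HR. Week-24 censoring applied to 37 to 47% of efgartigimod and 21 to 39% of placebo patients. Censored efgartigimod patients had median counts of 18 to 22, with a 10th percentile of 8 to 13, so a patient censored at 5 is in the tail.

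Two other calibrated settings extend the range:

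- **No intercurrent events:** HR 0.59 to 0.60 with all counts observed, 0.52 under Table 4 (1 − 0.52/0.59 = 11.9%; 1 − 0.52/0.60 = 13.3%). The efgartigimod KM median is 14 to 15 against 10, the placebo median at most 4 against 3, and about 39% of each arm has no row.
- **Modest intercurrent events:** HR 0.61 against 0.55 (9.8% lower), efgartigimod KM median 13 against 10, placebo unchanged.

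**Null.** With two identical arms of 78 and 39, Table 4 rejected in 5.1% of 2,000 trials.

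**The case against.** The strongest reply is that little depends on this analysis. It is outside the testing hierarchy (SAP 4.1.3.1). Cumulative weeks are estimated elsewhere, by the Hodges-Lehmann shift with its interval and by descriptive statistics. The treatment-policy, per-protocol and approach 2 analyses do not use Table 4, and type I error was not inflated in the null check. All of that stands, though the null check used arms alike in every respect, so it does not test arms with equal counts but different timing.

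Second, the missing row has a natural reading: if only control at week 24 is censored, a completer below 50 is an event at his or her count. That is reasonable, but the SAP does not say it, and the choice matters. In the fifth scenario the HR of 0.641 becomes 0.608 with these patients as events and 0.653 with them censored.

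Third, if the target is control until loss, a patient still in control has indeed not had the event, and censoring is legitimate. That is fair. It locates the fault in the cumulative time scale and argues for a calendar-time repair. Making everyone an event at the count would largely repeat the comparison the Mann-Whitney test already makes.

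A reader might infer that the treatment effect is always exaggerated, or that many patients certainly lack a rule. The documents support neither: the HR shift can reverse, and the share without a row cannot be derived from them.

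**Conclusion.** The defect stands in a limited form. The censoring rule depends on the outcome, its effect on the Kaplan-Meier curve has a certain direction, and Table 4 is incomplete. These conclusions follow from the SAP text alone.

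The size does not. Under the calibrated scenarios, with patients who fit no row as events, the efgartigimod Kaplan-Meier median rises by about 1 to 5 weeks, the placebo median by 0 to 1, and the HR is about 5 to 13% lower; roughly 12 to 39% of patients fit no row. The upper end of each range except the placebo median's lower bound comes from assuming no intercurrent events at all, although three of the five rows exist for them.

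Three stronger readings should be resisted:

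- That the first key secondary result is compromised. The Mann-Whitney test uses the uncensored count.
- That an inflated median will be reported. SAP 4.1.3 promises Kaplan-Meier estimates here and names a median only for time to platelet count response.
- That the distortion could be very large. Two arms given identical counts (median 6), one with control placed late and the other early, yield an HR of 0.25. That is a constructed extreme showing the mechanism, and nothing in the documents suggests such a pattern.

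The change is worth making because it is cheap, not because confirmatory inference is at risk.

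**What to change.** Preferred: put the analysis on a real time axis. Measure calendar time from the first count of at least 50×10⁹/L to a defined loss of control, with an event at 0 for patients who never reach 50 and censoring at day 169 for those still in control.

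Alternative, if the cumulative count is kept: drop the week-24 censoring and treat every count as observed, accepting that this adds little to the Mann-Whitney test.

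In either case:

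- add a row for completers not in control at week 24;
- define control at the end of treatment;
- state which row prevails when two apply;
- align the therapy-increase row with the main analysis, so that the start of a new concurrent ITP therapy is covered.

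The cost is the wording of Table 4 and reprogramming of the Cox and Kaplan-Meier outputs (Tables 14.2.2.2 and 14.2.2.3 in SAP 8.1). No new data are needed and the testing hierarchy does not change.

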4.1.2.3 OTHER SECONDARY ENDPOINTS (NOT ALPHA CONTROLLED)

All other secondary endpoints will be analyzed using the FAS on the overall population.

1) Overall Response: Proportion of patients with overall platelet count response defined as achieving a platelet count of $\geq 50 \times 109/L$ on at least 4 occasions at any time during the 24-week treatment period.

Derivation: a patient is considered a responder if he/she shows platelet count of at least 50×10^9 /L on at least 4 analysis visits during the 24-week treatment period. Platelet count after one of the main intercurrent events will be handled in the same way as for extent of disease control (section 4.1.2.2). Missing values not due to intercurrent events will be handled as described in section 4.1.2.5 (approach 1).

2) Extent of disease control defined as the number of cumulative weeks until week 12, with platelet counts of \geq 50×109/L.

SGS	Statistical Analysis Plan	
ARGX-113-1801	Final analysis	Final 1.0 of 28MAR2022

Derivation: total number of analysis visits during the treatment phase until week 12 with platelet counts of $\geq 50 \times 10^9$ /L. Platelet count after one of the main intercurrent events will be handled in the same way as for extent of disease control (section 4.1.2.2). Missing values not due to intercurrent events will be handled as described in section 4.1.2.5 (approach 1).

3) Proportion of patients with overall platelet response until week 12 defined as achieving a platelet count of $\geq 50 \times 10^9$ /L on at least 4 occasions at any time until week 12.

Derivation: a patient is considered a responder if he/she shows platelet count of at least 50×10^9 /L on at least 4 analysis visits during the first 12 weeks in the treatment period. Platelet count after one of the main intercurrent events will be handled in the same way as for extent of disease control (section 4.1.2.2). Missing values not due to intercurrent events will be handled as described in section 4.1.2.5 (approach 1).

- Mean changes from baseline for platelet count levels. Missing values will only be imputed for the Mixed Model for Repeated Measurements (MMRM). See section 4.1.3.6.
- 5) Mean changes from baseline in PRO/QoL:
 - a) *FACIT-Fatigue*: The FACIT-Fatigue Scale is a short, 13-item, easy to administer tool that measures an individual's level of fatigue during their usual daily activities over the past week. The level of fatigue is measured by recording item responses on a 4-point Likert scale ranging from 0 "not at all" to 4 "very much"

Total FACIT-Fatigue score¹⁰ = \sum individual scores (range between 0 and 52). The score for items [An5] and [An7] is reversed. A score of more than 30 indicates severe fatigue. The higher the score, the worse the QoL. A total score per analysis visit will be calculated. If 6 or more item scores are missing the total score will not be calculated. Otherwise, scores for missing items will be imputed with the arithmetic average of the non-missing item scores. A total missing score will only be imputed for the Mixed Model for Repeated Measurements (MMRM). See section 4.1.3.6.

b) *FACT-Th6*: The FACT-Th6 Scale is a 6-item tool rating the individual degree of concern with bleeding or bruising in the past 7 days. The level of concern is measured on a 4-point Likert scale (4 = not at all concerned to 0 = very much concerned).
SGS	Statistical Analysis Plan	
ARGX-113-1801	Final analysis	Final 1.0 of 28MAR2022

Total FACT-Th6 score¹⁰ = \sum individual scores (range between 0 and 24). All scores are reversed, except for item FACTTH61. A total score per analysis visit will be calculated. If 4 or more item scores are missing, the total score will not be calculated. Otherwise, scores for missing items will be imputed with the arithmetic average of the non-missing item scores. A missing total score will only be imputed for the Mixed Model for Repeated Measurements (MMRM). See section 4.1.3.6.

c) SF-36 (v2.0): The SF-36 is a 36-item scale constructed to survey healthrelated QoL on 8 domains: limitations in physical activities due to health problems; limitations in social activities due to physical or emotional problems; limitations in usual role activities due to physical health problems; bodily pain; general mental health (psychological distress and well-being); limitations in usual role activities due to emotional problems; vitality (energy and fatigue); and general health perceptions. SF-36 scores for the 8 subdomains, and norm-based physical and mental component summaries scores (P-CS and M-CS) will be calculated using a dedicated software: QualityMetric Health OutcomesTM Scoring Software 5.1. 2009 US population norm is used. Missing values are handled in the software: Scale scores can be computed if at least one item in the scale is answered. The Physical Component Summary (P-CS) score can be calculated when seven scale scores are available, and the Physical Functioning (PF) scale is not missing. The Mental Component Summary (M-CS) score can be calculated when at least seven scale scores are available, and the mental Health (MH) scale is not missing. QualityMetric's Missing Data Estimation chooses a unique scoring algorithm to apply to the calculation of the summary scores depending upon which particular scale score is missing from the eight scale profiles¹¹. More details on the calculation of SF-36 scores can be found in the OPTUM[®] PRO CoRE manual.

Missing scores will only be imputed for the Mixed Model for Repeated Measurements (MMRM). See section 4.1.3.6

6) Rate of receipt of rescue therapy: number of times rescue therapy is given per month, calculated as $\frac{\text{Total number of occurences}}{\text{total days in treatment phase}} \times 30.4$

Occurrence: a period of maximum 5 days where 1 or more rescue treatments are administered simultaneously or consecutively to the study patient. The start date/time of the occurrence is the start of the administration of the first rescue treatment. If this period exceeds the maximum of 5 days, a new occurrence will be assigned, with start date/time of the occurrence being the start date 5 days after the initial occurrence start date.

7) Proportion of patients for whom dose and/or frequency of concurrent ITP therapies have increased at week 12 or later.

Derivation: a patient is counted if (start date concurrent ITP therapy \geq target ADY of analysis visit corresponding to week 12) AND (dose > previous dose of the specific ITP therapy OR frequency > previous frequency of the specific ITP therapy OR new ITP therapy).

SGS	Statistical Analysis Plan	
ARGX-113-1801	Final analysis	Final 1.0 of 28MAR2022

8) Time to platelet count response defined as the time to achieve 2 consecutive platelet counts of $\geq 50 \times 10^9$ /L.

Derivation: It will be calculated as the difference between the first assessment date at which the condition '2 consecutive platelet counts $\geq 50 \times 10^9/L$ ' is fulfilled, taking into account all platelet count measurements (also the unscheduled ones), and first IMP intake date.

Time to platelet count response (days) = date (first assessment) – first IMP date + 1:

Response Situation	Time to Platelet Count Response	Outcome
No occurrence of platelet count of $\ge 50 \times 10^9/L$	Date of last available platelet count ^{***} – first IMP date ^{**} + 1	Censored
Early discontinuation of treatment (prior to W24) due to lack of efficacy or due to AE [*]	Early discontinuation date – first IMP date ^{**} + 1	Censored
Dose and/or frequency of concurrent ITP therapy increased*	Concurrent ITP therapy start date – first IMP date ^{**} + 1	Censored
Platelet count response	Date (first assessment) – first IMP date ^{**} + 1	Event

Table 5: Definition for Time to Platelet Count

* only applicable if the event (reaching platelet count response) has not occurred before

** or date of randomization for subjects not treated

*** or date of last contact for subject with no platelet count assessments

In case of rescue therapy, the platelet count cannot be used for 4 weeks after the initiation of the therapy (the initiation of the therapy is the start date/time of the administration of the first rescue treatment for that occurrence). The platelet count will be interpreted as $<50 \times 10^{9}$ /L for the 4 analysis visits following the initiation of the rescue therapy. Missing values not due to one of the main intercurrent events will be handled as described in section 4.1.2.5 (approach 1).

- 9) Extent of disease control defined as number of cumulative weeks over the planned 24-week treatment period with platelet counts:
 - a) $\geq 30 \times 109/L$ and at least 20×109/L greater than the baseline value

SGS	Statistical Analysis Plan	
ARGX-113-1801	Final analysis	Final 1.0 of 28MAR2022

Derivation: total number of analysis visits during the treatment phase with platelet counts of $\ge 30 \times 10^9$ /L and (platelet count – baseline platelet count) $\ge 20 \times 10^9$ /L. Platelet count after one of the main intercurrent events will be handled in the same way as for extent of disease control (section 4.1.2.2). Missing values not due to intercurrent events will be handled as described in section 4.1.2.5 (approach 1), but imputing with $\ge 30 \times 10^9$ /L / $< 30 \times 10^9$ /L and not with $\ge 50 \times 10^9$ /L / $< 50 \times 10^9$ /L. In the same way, if (platelet count – baseline platelet count) $\ge 20 \times 10^9$ /L for the previous and the next analysis visit, (platelet count – baseline platelet count) will imputed with $\ge 20 \times 10^9$ /L, otherwise with $< 20 \times 10^9$ /L.

The above will be repeated for the selection of patients where baseline platelet count $<15 \times 10^{9}$ /L.

b) $\geq 30 \times 10^9/L$ and at least $20 \times 10^9/L$ greater than the baseline value, where baseline platelet count $< 15 \times 10^9/L$.

10) Mean changes from baseline for:

Missing values will not be imputed.

Number of significant bleeding events where WHO bleeding scale ≥ 2 at any visit.

Derivation: total number of analysis visits for which WHO bleeding scale ≥ 2 . The overall score of the bleeding events per analysis visit will be used, calculated as the max bleeding scale over the different body systems available per analysis visit. The data will be used as is, without taking into account intercurrent events (treatment policy strategy). Missing bleeding assessments after one of the main intercurrent events will not be imputed. For 'increase of dose and/or frequency of concurrent ITP therapies or start of a new concurrent ITP therapy' and 'initiation of rescue therapy' the whole treatment period should be taken into account. In case of rescue therapy, the bleeding events will not be imputed for 4 weeks strictly after the initiation of the first rescue treatment for that occurrence). Missing values for reasons other than the main intercurrent events, will be imputed as described in section 4.1.2.5 (approach 3), but imputing as "scale >=2" instead of "bleeding" and as "bleeding scale<2" instead of "no bleeding".

